Before smoking the assigned research cigarette, participants will complete a **cigarette purchase task (CPT)**, a behavioral economics-based measure of cigarette reinforcement, which assesses hypothetical demand for cigarettes across a range of prices, and a **cross-price elasticity purchase task**, which assesses hypothetical demand for experimental cigarettes at increasing prices of an individual's preferred brand of cigarettes. Participants will also complete assessment of nicotine withdrawal and craving prior to smoking using the **Minnesota Nicotine Withdrawal Scale (MNWS)**¹⁵ and the **Questionnaire on Smoking Urges**¹⁶. Heart rate and blood pressure will be taken before smoking (some measurements may not be taken if sessions are completed remotely). After smoking, participants will complete assessments of subjective response to smoking with the **modified Cigarette Evaluation Questionnaire (mCEQ)**, the **Duke Sensory Questionnaire (DSQ)**, and the **Nicotine Drug Effects Questionnaire (NDEQ)**. Participants will also complete the MNWS again.

The **Predicted Behavior Questionnaire** will be asked at the beginning of Visits 3 and 4, prior to when the VLNC is smoked. It asks participants to indicate their intentions to use cigarettes and other tobacco products when cigarettes have lower nicotine content and come menthol or non-menthol flavor. The **Expected Utility Questionnaire** will also be administered at Visits 3 and 4, before participants smoke. This questionnaire asks the degree to which participants would use the study cigarettes they just smoked for the past week (menthol or non-menthol) would help them quitting, be less dangerous than smoking, give up tobacco use, smoker fewer cigarettes, etc.

Participants will report their perceptions of the health risks associated with both their usual brand and their study cigarette brand using the **Perceived Health Risks Assessment**.¹⁷

ECOLOGICAL MOMENTARY ASSESSMENT (EMA)

C.5 EMA Procedure. Participants will record cigarette smoking and alternative tobacco use, craving, symptoms of withdrawal, and subjective ratings (e.g., satisfaction, reward, craving reduction, physical sensations like throat hit) associated with smoking the most recent cigarette in response to 2 random prompts to their phone each day. We will use a mobile EMA application, in which participants answer a set of survey questions on their cell phone by selecting

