C.5.b. EMA Measures. EMA measurements will parallel the constructs used in the laboratory assessments (e.g., craving, subjective response) and have established psychometric properties.^{66,68,111,150-154} Subjective ratings will be queried using items from the mCEQ, which has been pilot tested for EMA deployment by the PI and is being deployed via EMA for her ongoing R01. Questions will also assess the use of alternative tobacco products since the previous assessment, characterizing flavors (e.g., fruit, chocolate), use of usual brand cigarettes, craving, withdrawal, and factors associated with smoking (life events, mood, peer use, alcohol, other drug use) that have been used in prior EMA studies by the PI and others. To minimize response burden, EMA will prompt use-relevant probes via skip patterns. Missed EMA assessments will be retrospectively assessed by phone or online via a REDCap survey.

Following are the standard procedures that have been adopted for OUM/OUHSC for all studies that will be facilitated in-person and would be utilized for this study in response to COVID-19.

PROCEDURE:

1. Employees will comply with all OUHSC COVID related policies and procedures as currently exist and as are revised in the future.
2. Efforts will be made to minimize face-to-face time with participants. When possible, consents will be sent to participants at their homes and reviewed by phone or zoom, as available. Additional items, including pregnancy tests, will also be shipped to the home, and reviewed over phone or zoom, when possible.
3. During scheduling, participants will be asked to wear a mask, if they have one available, to their appointments. For participants who do not have access to a face mask, one will be provided. They will also be asked the questions from the OUM/OUHSC COVID19 Questionnaire (see attached in “Other Documents”).
4. If the patient is symptomatic or has known direct contact with a person with COVID-19 they will not be able to attend a study session and will be asked to consult with their PCP prior to re-scheduling the visit.

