Participants will be involved in the study for approximately 2 months. There will be 5 in-person study visits (or virtual sessions) and a total of 21 days of daily monitoring of cigarette smoking behavior. There will be a 30-day follow-up after visit 5, that will be conducted either in person or over the telephone.

4. Describe blinding, including justification for blinding or not blinding the trial.

We considered blinding participants to the nicotine content in the research cigarettes to minimize the possibility that perceptions of these cigarettes may impact ratings of appeal/reinforcement and use behavior (e.g., compensatory behavior). We ultimately chose not blind participants so that we could model real-world conditions in which participants would be aware of the nicotine content of the cigarettes they smoke. [name], our consultant, is taking this same approach (e.g., not blinding participants) in a pilot study conducted as part of her U54. While we know about responses to VLNCs in a blinded scenario, findings from our study will be one of the first to inform VLNC work in an un-blinded scenario with young people.

5. Include justification for inclusion of a placebo or non-treatment group.

N/A. This is not a treatment study.

6. Describe what happens to participants receiving therapy when study ends or if their participation in the study ends prematurely.

N/A. This is not a treatment study.

7. Indicate where the procedures will be completed.

All participant recruitment, enrollment and testing will occur at the research laboratory of the TSET Health Promotion Research Center (HPRC) in Oklahoma City, OK. HPRC has conducted smoking research for the past 5 years.

8. Indicate whether clinically relevant research results, including individual research results, will be disclosed to participants. If so, under what conditions?

Females will be asked to take a pregnancy test at each in-person (or virtual) session prior to smoking, to determine eligibility. If a woman is pregnant, she will be given the results of her test immediately. If the session is completed remotely,

pregnancy tests will be provided to the participant before the session (mailed or curb-side pick-up) and pregnancy will be confirmed prior to beginning a smoking session.

9. Identifiers might be removed and the de-identified information may be used for future research without additional informed consent from the subject.

D. Biospecimens

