Primary Outcomes: (a) The relative reinforcing value (RRV) of usual brand cigarettes vs menthol VLNCs; (b) RRV of non-menthol VLNCs vs menthol VLNCs. RRV will be operationalized as within-subject differences in subjective ratings of cigarette appeal/reinforcement (satisfaction, reward, craving reduction, physical sensations) during each ad libitum smoking session. Secondary Outcomes: (a) CO boost; and (b) puff topography (number of menthol versus non-menthol cigarette puffs consumed, number of minutes smoked, interval between puffs).

Analysis of covariance will be conducted to examine effects of cigarette type (usual brand, menthol VLNC, non-menthol VLNC) on the outcomes of interest, controlling for cigarettes per day (CPD), nicotine dependence, race/ethnicity, gender, and age of smoking onset as potential covariates. Factors related to study drop-out and differences in cigarette compliance will also be examined as potential covariates. Exploratory analyses will examine differential reactions to usual brand and each research cigarette by race/ethnicity (White, Black, Hispanic, Other) and by gender. Significant interactions will be followed up with individual contrasts of cell means using Fisher's Least Significant Difference tests. We will examine whether topography differs as a function of in-person versus remote session.

3. EMA Analyses (Aim 2)

Primary Outcomes: (a) within-day subjective response (craving reduction, satisfaction, psychological reward, physical sensations like throat grab) to the most recent cigarette smoked; (b) within-day number of research cigarettes smoked per day; (c) within-day number of non-research cigarettes smoked; and (d) within-day withdrawal intensity. Secondary Outcomes: (a) within-day use of alternative tobacco products; (b) changes over the course of days (creating an average change score for each person) for each outcome; (c) number of days abstinent from tobacco use.

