Patterns of missing data, compliance, distributional properties of variables, and correlations among all measures will be assessed. We will control for potential variables related to missing data and utilize multiple imputation methods (expectation maximization algorithm).¹⁶⁰⁻¹⁶³ Analysis will use linear mixed modeling with random subjects effects^{164,165} to assess the main effect of cigarette type on the primary and secondary outcomes of interest. Models will use a contrast to compare differences between menthol VLNC and non-menthol VLNC at the day-level on predictions of the outcome of interest and that outcome of interest at time t (e.g., morning) predicting behavior (number of cigarettes, any smoking, craving, withdrawal) occurring at a subsequent time point (controlling for cigarette consumption from the previous report). Comparison of usual brand and the menthol VLNC ratings will also be made to determine the perceived similarity of the VLNC to one's own brand. A sub-group of respondents may have fixed (unchanging) ratings of subjective response, craving, cigarettes per day, or withdrawal over the course of 7 days, although this is unlikely given the team's previous research. We will examine baseline and daily factors that set "no changers" apart from those whose show fluctuations in these factors, and examine these as potential covariates in models. Within-person slopes capturing associations between cigarette type and the EMA outcome of interest will be saved in regression models and used to predict the ETM responses.

4. ETM Analyses (Aim 3)

Primary Outcomes: (a) consumption of alternative tobacco products (milligrams of nicotine for alternative tobacco sources) as a function of cigarette type available. Typically, as cigarette price increases, consumption of other tobacco products increases.¹⁴ Secondary Outcomes: (a) breakpoint: the first price at which consumption of the available cigarette is zero; (b) intensity of demand: consumption at the lowest price); (c) elasticity of demand: sensitivity of cigarette consumption to increases in cost, (d) Omax: maximum expenditure for cigarette type available; and (e) Pmax: price at which expenditure is maximized.

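### The plan names the EM algorithm as its multiple imputation method for EMA data, and states no draws, multilevel imputation model or pooling rule

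*Combined protocol and SAP*

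**What the plan says.** Section J.3, EMA Analyses (Aim 2), has one clause on filling in missing data: the team will "utilize multiple imputation methods (expectation maximization algorithm"). Just before it the plan says "We will control for potential variables related to missing data", without naming the variables. The analysis model follows: "Analysis will use linear mixed modeling with random subjects effects".

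The four primary outcomes are "within-day subjective response (craving reduction, satisfaction, psychological reward, physical sensations like throat grab) to the most recent cigarette smoked", research cigarettes smoked, non-research cigarettes smoked, and withdrawal intensity. The same section plans lagged models, in which a report at one time predicts behaviour at a later time. It also says "Within-person slopes capturing associations between cigarette type and the EMA outcome of interest will be saved in regression models", and these slopes are then used to predict ETM responses (J.4).

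Section C.5 sets the data volume: EMA reports are given "in response to 2 random prompts to their phone each day". The section on duration and visits gives "a total of 21 days of daily monitoring of cigarette smoking behavior". Section C.5.b adds a recovery step: "Missed EMA assessments will be retrospectively assessed by phone or online via a REDCap survey".

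No expected share of missed prompts, imputation model, number of imputed data sets, pooling rule or software is stated.

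**The concern.** The clause joins two different procedures. Multiple imputation draws several plausible values for each missing item, analyses each completed data set, and pools the results so that uncertainty about the missing values reaches the standard error. EM maximises a likelihood; when used to complete data, it supplies one fitted value per gap. It can be one component of genuine multiple imputation, but is not sufficient for it.

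An analyst who follows J.3 literally could fill EM values once and fit the mixed model as if every prompt had been answered. Standard errors for the menthol versus non-menthol VLNC contrast would then be too small. An analyst who runs pooled imputation with a routine that treats prompts as independent rows would have a different problem. The imputed ratings would ignore which person they belong to, which harms the within-person contrast and the person-specific slopes passed to the ETM regressions.

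**Working it through.** The plan attaches no figure to its imputation, so there is none to reproduce.

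**Inputs from the documents.** Prompts per person: 2 × 21 = 42, or 42 / 3 = 14 per condition. Analytic n = 100 (J.1).

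**Assumptions.** Two-sided alpha 0.05; missing share m from 5% to 30%; prompts missing completely at random; within-person SD 1.

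**A. Single fill, no person-by-condition variation.** Let σ² be the within-person variance and P = 14. For the contrast between two conditions:

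- True variance on observed prompts: 2σ² / [nP(1−m)].
- A conditional-mean fill leaves the estimate essentially unchanged, restores the row count to nP, and shrinks the residual variance to about σ²(1−m). Reported variance: 2σ²(1−m) / (nP).
- Reported SE / true SE = 1−m. Actual type I error = 2[1−Φ(1.96(1−m))].

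At m = 0.15: true SE = √(2 / (1400 × 0.85)) = 0.0410; reported SE = √(2 × 0.85 / 1400) = 0.0348; ratio 0.85.

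| Missing share | SE ratio | Type I error |
|---|---|---|
| 5% | 0.95 | 6.3% |
| 10% | 0.90 | 7.8% |
| 15% | 0.85 | 9.6% |
| 20% | 0.80 | 11.7% |
| 30% | 0.70 | 17.0% |

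A simulation (n = 100, 3 × 14 prompts, between-person SD 1, no true difference, 1,200 trials per scenario) agrees. Each cell gives SE ratio and type I error:

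| Scenario | Observed data, no imputation | Single fill | Proper MI, 20 data sets |
|---|---|---|---|
| 15% of prompts missing | 0.99; 5.5% | 0.83; 10.2% | 0.99; 5.8% |
| 30% missing | 0.99; 5.8% | 0.68; 18.2% | 0.98; 5.5% |
| 15% missing, and 20% of people lose one VLNC week | 1.03; 4.7% | 0.77; 13.3% | 1.02; 4.8% |

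**B. Single fill, with person-by-condition variation.** The result depends on the fill and analysis models:

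- Fill model with person and person-by-condition effects, analysed by person-level contrasts, person-by-condition SD 0.5: type I error 6.2% at 15% missing and 6.1% at 30%.
- Fill and analysis with person effects only, SD 0.3: type I error is already 14.3% (15% missing) and 14.2% (30% missing) without any fill, because the model lacks condition slopes. The fill raises it to 21.5% and 32.5%.

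**C. Pooled multiple imputation that ignores person.** In simulation, the reported SE of the contrast was about 19% larger than in the observed-data model at 15% missing and about 30% larger at 30%. If cigarette type was also left out of the imputation model, the menthol contrast shrank by about the missing share.

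**The case against.** The strongest reply is that the plan says multiple imputation and never says one filled data set. EM with bootstrap draws, or EM estimates as starting values for data augmentation, are recognised routes to multiple imputation. With Rubin pooling they can give valid standard errors. The clause carries citation numbers 160 to 163, while the reference list supplied ends at 27, so the intended routine cannot be traced. This stands. A reader might infer that the plan commits to a single fill and that the Aim 2 standard errors will be too small; the documents do not support that unconditional reading.

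The size is also open. The figures in A require no person-by-condition variation, yet the plan to save person-specific slopes suggests that some is expected. Retrospective recovery (C.5.b) reduces what has to be imputed, by an amount that is not given. This stands too, though B shows that such variation does not always soften the effect.

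A further tempting inference is that imputation adds nothing because the mixed model already uses every observed prompt. That is fair for missing outcomes in the cigarette-type contrast under MAR. It fails for the lagged models, where a missed prompt is a missing predictor and an observed-records analysis drops the row.

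What does not stand is treating the clause as mere brevity. It names a method, and that method alone does not do what the label says.

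**Conclusion.** The concern holds as a mis-specified method, worth correcting before the main outcome analyses. J.3 presents EM as multiple imputation, and nothing elsewhere supplies the draws, multilevel structure or pooling that would make it so.

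The consequence is conditional:

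- **EM values filled once:** standard errors are understated by about the missing fraction when people do not differ in their response to cigarette type. With such differences, the size depends on the fill and analysis models.
- **Pooled EM-based imputation:** standard errors can be valid, but ignoring the nesting costs precision and can dilute both the contrast and the slopes used for the ETM models.

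The missing shares, the variance components and data missing completely at random are assumptions; the documents give none of them.

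**What to change.** Replace the imputation clause in J.3 with wording to this effect:

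*The primary cigarette-type contrast for each Aim 2 outcome is estimated by the likelihood-based mixed model on all observed EMA records, assuming data missing at random, with variables related to missingness as covariates and no imputation. Where imputation is used (lagged models with missing predictors, or sensitivity analyses), it will be multilevel multiple imputation with at least 20 data sets. The imputation model will include cigarette type, period and person effects. Results will be pooled by Rubin's rules, and the imputation will be carried through to the saved within-person slopes.*

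This works whichever procedure was intended. In the simulations under A, the observed-data analysis kept type I error between 4.7% and 5.8%. Data collection and sample size do not change. The cost is plan wording and a little more analysis work for the lagged and sensitivity models; the primary contrast becomes simpler.

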Visit 5 (Experimental Tobacco Marketplace)	\$ 50
Bonus for eligible referral	\$20
Bonus for scheduling and attending first visit within 5 days of phone screening	\$20
EMA	

Call completion (*42 calls)	\$1/call (\$42 total)
Bonus for completing all calls each week (* 3 weeks)	\$10/week (\$30 total)
Bonus for completing 85% of calls for 3 weeks	\$45
Total possible EMA	\$117
Research Cigarette Compliance	
Returned used cigarettes	\$7 maximum/week @ 2 weeks
Returned unused cigarettes (\$0.25/cigarette)	\$20 maximum/participant
Returned empty packs (\$1/pack)	\$5 maximum/participant
Total possible cigarette compliance	\$14 + \$20 + \$5 = \$39
30-Day Follow-up	
30-day Follow-Up + ETM 3	\$45
Travel for In Person or Curbside Pick-up/Drop-Off	
\$10 for each in person visit/curbside pick-up/drop-off of study materials @ 4 visits	\$40 maximum/participant
Bonus for completing all phases	\$ 70
Maximum Total	\$ 571

To enhance retention in all phases of the study, due to higher than anticipated loss-to-follow-up, we will offer a bonus of missed incentive amounts to participants who are hard-to-reach or schedule. With this bonus, participants will be eligible to receive missed compensation opportunities, if they complete remaining in-person study sessions and/or surveys. Missed opportunities may include the bonus for scheduling and attending the first visit within 5 days of phone screening (\$20), the eligible referral bonus (\$20), bonuses for completing all EMA surveys each week (\$30 maximum) even if they miss some surveys, bonus for completing 85% of EMA surveys for 3 weeks (\$45) even if they miss some surveys, and the bonus for completing all phases of the study (\$70). Enhancement bonuses will be separated into \$20 increments to encourage a participant to attend any remaining session(s) they have not completed. After the final in person session is complete, the participant will be eligible for all remaining compensation amount not already claimed, up to the maximum of \$571, even if they may not have met the full criteria. Thus, we calculate their maximum bonus amount allotted to participant, and give it to them in \$20 increments (per number of sessions attended). When they complete the final in-person visit, they are eligible for all remaining bonus/compensation to get the maximum amount (\$571).

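### J.3 names only random subject effects for the Aim 2 mixed model; an intercept-only fit is permitted and would understate the SE of the menthol versus non-menthol contrast if responses vary by person and cigarette or are serially correlated

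*Combined protocol and SAP*

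**What the plan says.** Section J.3 (EMA Analyses, Aim 2) sets out the model in one sentence: "Analysis will use linear mixed modeling with random subjects effects", used "to assess the main effect of cigarette type on the primary and secondary outcomes of interest". The key comparison follows: "Models will use a contrast to compare differences between menthol VLNC and non-menthol VLNC at the day-level". J.3 also plans person-specific cigarette-type effects: "Within-person slopes capturing associations between cigarette type and the EMA outcome of interest will be saved in regression models". These are carried into the Aim 3 regressions in J.4. It further foresees, while calling it unlikely, that "A sub-group of respondents may have fixed (unchanging) ratings of subjective response, craving, cigarettes per day, or withdrawal over the course of 7 days".

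The data structure is given elsewhere. C.5 (EMA Procedure) has participants reporting "in response to 2 random prompts to their phone each day". The item on duration and number of visits gives "a total of 21 days of daily monitoring of cigarette smoking behavior", and the compensation table lists "Call completion (*42 calls". Under Aim 1 and the Visit 2 procedures, each VLNC type is smoked in one 7-day period. The order is counterbalanced and a 7-day wash-out separates the periods.

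For this model, section J states no random cigarette-type slope, no person-by-period or person-by-condition term, no residual correlation structure, no robust standard error and no degrees-of-freedom method.

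**The concern.** Cigarette type never changes within a block. Anything that shifts a person's whole block goes straight into the contrast and does not average out over the prompts in that block. Examples are a personal liking for one cigarette, an unusual week, or poor compliance with one product. A random subject intercept cancels from a within-person contrast, so it cannot absorb such shifts. Serial correlation between neighbouring prompts has a similar effect, because 14 correlated reports carry less information than 14 independent ones.

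The plan gives reason to expect such variation. Saving person-specific slopes to predict marketplace responses is useful only if the type effect differs between people. The lagged models in J.3 presume that one report predicts the next. J.2 and J.5 look for moderators of the cigarette effect, and C.4.e examines differences in noncompliance between cigarette conditions.

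At stake is the comparison of the two VLNCs on the Aim 2 primary outcomes. The confidence intervals could be too narrow and the false-positive rate above the nominal level.

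**Working it through.** **Inputs from the documents.** Two prompts a day (C.5), 21 monitored days (duration item), 42 prompts in all (compensation table). There are three conditions: usual brand, menthol VLNC and non-menthol VLNC.

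**Reproducing the plan's figures.** 3 weeks × 7 days × 2 = 42 prompts, which matches, so there are m = 14 per condition. J.1 gives n = 100 for power 0.8. That cannot be recomputed, because no effect size, SD, alpha or sidedness is stated. It does not matter here, since n cancels from the ratio below.

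**Assumed inputs, absent from the documents.** Residual variance is set to 1. Person-by-cigarette variance is τ² = 0.05, 0.10 or 0.20. As a separate case, first-order autocorrelation ρ = 0.3 between consecutive reports. All prompts are answered, and the test is two-sided at 5%.

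**Step 1, true variance of the contrast.** Let D = 1 + 2Σ(1 − j/m)ρ^j, summed over j = 1 to m − 1, so D = 1 when ρ = 0. Then

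Var(true) = (2/n)(τ² + D/m) = 2(D + mτ²)/(nm).

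**Step 2, variance reported by an intercept-only fit.** This is 2·MSE/(nm). With k = 3 conditions, MSE pools, per person, k − 1 = 2 df with expectation D + mτ² and k(m − 1) df with expectation W = (m − D)/(m − 1). When ρ = 0, W = 1. For m = 14 that is 2 + 39 = 41 df; for m = 7 it is 2 + 18 = 20 df.

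**Step 3, ratio and error rate.** SE ratio R = √[(D + mτ²)/MSE]. Type I error = 2[1 − Φ(1.96/R)].

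Worked case, m = 14, τ² = 0.10, ρ = 0: D + mτ² = 1 + 1.4 = 2.4. MSE = (2 × 2.4 + 39 × 1)/41 = 1.068. R = √(2.4/1.068) = 1.50. Type I error = 2[1 − Φ(1.31)] = 19.1%.

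| Unit | τ² | ρ | D + mτ² | MSE | R | Type I error |
|---|---|---|---|---|---|---|
| Prompt, m = 14 | 0 | 0 | 1.00 | 1.000 | 1.00 | 5.0% |
| Prompt, m = 14 | 0.05 | 0 | 1.70 | 1.034 | 1.28 | 12.6% |
| Prompt, m = 14 | 0.10 | 0 | 2.40 | 1.068 | 1.50 | 19.1% |
| Prompt, m = 14 | 0.20 | 0 | 3.80 | 1.137 | 1.83 | 28.4% |
| Prompt, m = 14 | 0 | 0.3 | 1.77 | 0.981 | 1.34 | 14.4% |
| Day, m = 7 | 0.05 | 0 | 1.35 | 1.035 | 1.14 | 8.6% |
| Day, m = 7 | 0.10 | 0 | 1.70 | 1.070 | 1.26 | 12.0% |
| Day, m = 7 | 0.20 | 0 | 2.40 | 1.140 | 1.45 | 17.7% |

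In the day rows, τ² is a share of day-level residual variance. If day values are averages of two independent prompts and the share is defined per prompt, the larger figures roughly carry over.

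**Step 4, simulation check.** With 2,000 runs per setting and 14 prompts per condition, the intercept-only test rejected in 13.9%, 17.9% and 28.9% of runs for τ² = 0.05, 0.10 and 0.20, and in 14.6% for ρ = 0.3 alone. A paired test on person-week means rejected in 4.4% to 5.7%.

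**The case against.** The strongest reply is that J.3 never says the model is intercept-only. It speaks of random effects in the plural and does not mention independent residuals. The saved cigarette-type slopes could come from a random slope in this same model, which would largely meet the point. A reader might infer that the plan commits to an invalid test, or that it contradicts itself by saving slopes its model cannot produce. The documents support neither: a random slope is not excluded, and the slopes could also come from separate regressions for each person.

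A reader might also infer that a random subject effect ignores within-week correlation altogether. It does not. It models the correlation common to all of a person's reports and misses only the extra correlation within a condition-week.

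The size is also open to challenge. No variance component is given, the day-level wording may halve the number of units per condition, and smaller shares do less harm: a 1% to 2% share with 14 prompts gives 6.5% to 8.1%.

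These points stand, and they make the finding conditional. They do not remove it. The only covariance component written down is the subject effect, an intercept is its ordinary reading, and nothing elsewhere in section J prevents that fit.

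**Conclusion.** The point holds as a conditional one. As written, J.3 permits a random-intercept fit whose standard error for the menthol versus non-menthol contrast is too small if the cigarette effect differs between people or reports are serially correlated within a week.

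Under assumed person-by-cigarette variance of 5% to 20% of residual variance, the standard error is too small by a factor of about 1.3 to 1.8 with 14 prompts per condition, and a nominal 5% test runs at about 13% to 28%. With the day as unit and day-level shares, the rate is about 9% to 18%. The test holds 5% only if both sources are zero, which sits poorly with the plan's own interest in person-specific slopes. Full response and equal variance in all three conditions are assumed throughout. It cannot be said from the documents that the standard error will be wrong, or by how much.

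**What to change.** In J.3, add to the random subject intercept a random subject-by-cigarette-type (condition-week) effect, or equivalently a random cigarette-type slope. Allow for within-week serial correlation through either an autoregressive residual or person-clustered robust standard errors. Name a paired analysis of person-week means as the fallback if the model does not converge; in the simulation it kept the error rate close to 5%. A particular degrees-of-freedom method is not needed for validity. It would help to state whether the unit of analysis is the prompt or the day, and whether the slopes used in J.4 come from this model.

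The change needs only analysis-plan wording, with no new data or participants. The downsides are wider confidence intervals and possible convergence problems. If the team already intends a random slope, one sentence settles the main part.
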